4.5 Expected Trial Duration

We expect to be able to enroll 14,500 newborns within 1.5 to 2 years (**Table 3**).

Table 3. Trial timeline with 14,500 enrollments

Period	2026	2027	2028	2029	2030	2031
Events	Enrolment of 14,500 children					
Assessment for morbidity and mortality to 6 weeks	Ongoing	Ongoing	Assessment completed			
Assessment for neurodevelopmental outcomes by 5 years of age					Ongoing	Assessment completed
Assessment for AD by 2 years of age	Ongoing	Ongoing	Ongoing	Ongoing	Assessment completed	

Follow-up will be until 2 years of age for mortality/morbidity. Follow-up for the primary outcome will be finished ~2 years after trial initiation (~1½ years of enrolment with primary follow-up assessed at 6 weeks), while secondary follow-up for morbidity, mortality and AD will continue to 2 years of age. The first 500 children recruited from the HDSS will be followed to 5 years of age for neurodevelopmental outcomes. For this reason, the trial data collection should be finished within <7 years.

4.6 Planned seroprevalence substudies nested in the trial

To further shed light on the combined impact on overall health of providing HBV0, we plan to conduct 2 serosurveys, pending separate approval from the Guinea-Bissau ethics committee:

1. Prevalence of HBsAg among women given birth in Bissau.

A previous study from 2014-2016 indicated a 15% prevalence of HBsAg in women.[45] Using a rapid diagnostic test (RDT) for HBsAg (such as [54]) with a drop of blood collected by finger prick, we will assess the prevalence of HBsAg. If the prevalence is ~15%, a sample of 250 RDTs is required to measure the prevalence with a 95% confidence interval of +5% (e.g., 14% to 24%). The HBsAg serosurvey will be done under separate informed consent. For mothers who test positive, we will ensure that their newborns are offered HBV0 vaccine, alongside BCG and OPV, to prevent vertical transmission of hepatitis B.

2. Prevalence of HBsAg among children enrolled in the trial by 1 year of age.

At the 1 year HDSS follow-up procedure, we will offer the family that their child participates in a serosurvey where we will measure the prevalence of HBsAg using an RDT.[54] Provided informed consent, we will sample at least 250 children and if the true prevalence of HBsAg is 13%, this will give us power to detect the actual prevalence with a precision of +4%.

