A systematic Cochrane review of RCTs has shown that HBV0 reduces vertical transmission by 72% (60%-80%), but noted limited data on adverse events.[29] The use of HBV0 is especially important in countries with a high prevalence of hepatitis B surface antigen (**HBsAg**), yet WHO recommends universal HBV0 (including in neonates with a birth weight <2,000g and premature neonates), also in high-income countries.[27] While Australia, New Zealand and Japan have a universal HBV0 policy, most European countries only provide targeted HBV0 to babies born to HBsAg-positive mothers.[30] In the US, the policy was recently updated so that HBV0 is no longer recommended to newborns born to a mother that tested negative for HBsAg.[31] Only 15 of 47 countries in the WHO Africa region have implemented HBV0 due to logistical and contextual barriers and the lack of benefit when the mother is HBsAg-negative.[28,32]

[figure not shown]
The Health Ministry in Guinea-Bissau is planning to add HBV0 to the newborn vaccination program in 2028, in addition to the currently recommended BCG and OPV. Notably, since most African countries including Guinea-Bissau have no hepatitis B screening program, HBV0 is given to all neonates, even though it is only needed by those whose mothers are hepatitis B carriers. The majority of children are well protected against horizontal transmission by the three HepB vaccines included in the pentavalent vaccines provided at 6, 10 and 14 weeks of age. This makes it particularly important to ensure that there are no negative effects of HBV0.

HBV0 and non-specific effects

Hepatitis B vaccine was developed in 1982[27] and it has never been investigated whether HBV0 is associated with NSEs – beneficial or detrimental (**Figure 1**).

Figure 1. Effects on overall health of at-birth vaccines recommended by WHO.

Overall health effects in Guinea-Bissau of vaccines recommended at birth by WHO

This is a critical evidence gap for an effective and universally recommended intervention, particularly since two observational studies from West Africa have suggested that HepB vaccines provided later in infancy may be associated with negative NSEs.[33,34] In line with what has been seen for other non-live vaccines, this was particularly the case among females.[33,34]

HBV0 and atopic dermatitis

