In a small cross-sectional study utilizing blood samples from children aged 18 months, who were born before HBV vaccination was introduced in Guinea-Bissau in 2008 as part of the pentavalent vaccine series, 11% (21/187) were infected with Hepatitis B (HBsAg-positive) and 5% had recovered from infection.[45] A population-based study conducted by BHP between 2014-2016 reported a high (18.7%, 15% in women, 24% in men) prevalence of HBsAg among adults in urban Bissau[46], making vertical transmission a relevant public health concern which could be addressed by HBV0 vaccination. The Ministry of Health in Guinea-Bissau plans to introduce HBV0 for all newborns in 2028. There is therefore a **unique window of opportunity to conduct a large-scale RCT evaluating the overall health effects of HBV0** before vaccination becomes national policy. The proposed trial would address the significant knowledge gap regarding the overall health effects of HBV0.

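### Serosurvey planning figures in section 4.6: the 14% to 24% interval does not belong to a 15% prevalence, and the 13% for trial children sits badly with the protocol's own data and ignores the randomised arms

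*Protocol*

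**What the plan says.** Protocol section 4.6 describes two nested surveys that still await separate ethics approval.

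- **Survey 1, women giving birth.** The planning value is introduced by "A previous study from 2014-2016 indicated a 15% prevalence of HBsAg in women.[45"]. At about that prevalence, the plan says, "a sample of 250 RDTs is required to measure the prevalence with a 95% confidence interval of +5% (e.g., 14% to 24" percent.
- **Survey 2, trial children at the 1-year visit in the surveillance area.** At least 250 children are to be tested, and "if the true prevalence of HBsAg is 13%, this will give us power to detect the actual prevalence with a precision of +4" percent. One sample size, one prevalence and one precision are given. Randomised arm is not mentioned.

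Section 2.1 supplies the figures to compare with:

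- The adult survey "reported a high (18.7%, 15% in women, 24% in men) prevalence of HBsAg among adults in urban Bissau[46"].
- In children aged 18 months who were born before hepatitis B vaccination was introduced, "11% (21/187) were infected with Hepatitis B (HBsAg-positive").
- From a systematic review, "HBV0 reduces vertical transmission by 72% (60%-80" percent).

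The bare plus signs are read here as plus or minus. The sign may have been lost when the text was extracted, and nothing below depends on it.

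**The concern.** In survey 1 the assumed prevalence and the example interval cannot both be right: an interval of 5 points either side of 15% runs from 10% to 20%. If the interval was worked out for another population, the stated number of tests may have been too.

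In survey 2 the planning value is higher than the protocol's own figure for children with no hepatitis B vaccination at all. Trial children are scheduled for three HepB doses from 6 weeks of age, and half of them are randomised to HBV0. A single figure over a 1:1 mixture of two schedules also describes neither schedule.

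The stakes are modest. Section 2.2 says that any broader effects must be weighed against the known benefit of HBV0, and section 4.6 presents the surveys as a contribution to that picture. Neither Table 2 nor section 8.2 contains an HBsAg outcome, so survey 2 is the one place in the document where infection could be set out by randomised schedule.

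**Working it through.** **Formulas.** For one proportion, half-width = 1.96 × √(p(1−p)/n), and n = 1.96² × p(1−p)/d².

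**Survey 1: trying to reproduce 250 and 14% to 24%**

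- p = 15%, n = 250: 1.96 × √(0.15 × 0.85/250) = 4.4 points, so 10.6% to 19.4%. The Wilson interval is 11.1% to 20.0%, and the exact interval for 38/250 is 11.0% to 20.3%. None is close to 14% to 24%.
- p = 15%, d = 5 points: n = 1.96² × 0.1275/0.0025 = 196, not 250.
- The midpoint of the printed interval is (14 + 24)/2 = 19%.
- p = 18.7% (men and women together, section 2.1), n = 250: half-width 4.8 points. The simple interval is 13.9% to 23.5%, Wilson 14.4% to 24.0%, and exact (47/250) 14.2% to 24.2%. These match the printed interval.
- At 18.7% or 19%, 5 points either side needs 234 or 237 tests. So 250 is a rounded-up figure on that basis, and more than enough at 15%.

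**Survey 1: citation.** Section 4.6 credits the 15% in women to reference 45. Section 2.1 credits it to reference 46. Reference 45 is the study of 18-month-old children.

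**Survey 2: precision**

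- p = 13%, n = 250: 1.96 × √(0.13 × 0.87/250) = 4.2 points, which rounds to the stated 4. The plan's figure is reproduced.
- p = 11%, n = 250: 3.9 points. A lower prevalence makes the absolute interval narrower.

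**Survey 2: the 13% against the protocol's own figures**

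- 21/187 = 11.2%, with an exact 95% interval of 7.1% to 16.7%. The interval includes 13%, so this study alone does not rule it out.
- Generous bound on vertical infection: take 15% maternal prevalence, suppose that every exposed child without HBV0 is infected, and apply the 72% reduction to the HBV0 half. Over both arms this gives 15% × (1 + 0.28)/2 = 9.6%. For reductions of 80% and 60% it gives 15% × (1 + 0.20)/2 = 9.0% and 15% × (1 + 0.40)/2 = 10.5%.
- The same in reverse, applying the reduction to all infection as an illustration: an overall 13% requires 2 × 13%/(1 + 0.28) = 20.3% in controls (18.6% to 21.7% for reductions of 60% to 80%). That is above the assumed maternal prevalence.
- Section 2.1 states that most children are well protected against horizontal infection by the three later HepB doses, so that route is unlikely to fill the gap.

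**Survey 2: what one figure over both arms would mean**

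- Illustrative assumption: controls at 11%, HBV0 children at 0.28 × 11% = 3.1%. The overall figure is (11 + 3.1)/2 = 7.0%, which describes neither arm.
- With about 125 children per arm, the half-width of the difference is 1.96 × √(0.11 × 0.89/125 + 0.0308 × 0.9692/125) = 6.3 points around a difference of 7.9 points. At these values Fisher's exact test has about 61% power, so a comparison by arm is descriptive.

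**The case against.** The survey 1 error lies in an illustrative interval. The sample exceeds what the stated aim needs, so nothing is undersized. This stands, and it limits the point to a correction of text.

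The 13% is conditional, comes with correctly computed precision, and lies inside the confidence interval of the small 11% study. A lower true value would only tighten the absolute interval. This also stands: 13% is a cautious choice for sizing. What remains is that no source is given and that it fits poorly with the protocol's other figures. The exclusion of infants of known carriers adds little to that argument, because section 2.1 says there is no national screening programme and few carriers will be known.

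A reader might go further and infer that survey 2 pools the arms, discards the randomised comparison and so cannot show the benefit of HBV0. The document does not say this. Section 4.6 is silent about arms, each child's allocation is recorded on the inclusion form, and a report by arm is not ruled out. A reader might also infer that the weighing of benefit and harm depends on this survey. Sections 2.2 and 12 treat the specific benefit as already established, and no objective asks the trial to measure it. Nor should a range of power figures be quoted against the survey: the protocol plans no test between arms, and at low prevalence the expected counts are too small for the usual normal approximation.

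**Conclusion.** The point holds as a minor correction.

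- **Survey 1:** the stated interval is wrong for the stated prevalence. It should be about 10.6% to 19.4% with 250 tests, and 5 points either side needs 196. The printed interval most probably comes from the 18.7% all-adult figure. That origin is an inference from the match, not something the document states. The citation for the 15% disagrees with section 2.1.
- **Survey 2:** the arithmetic is right to rounding. The 13% is unsupported and hard to reconcile with 11% before vaccination, or with the bound of 9.6% for vertical infection over both arms. That bound assumes 15% maternal prevalence, a 72% reduction and no horizontal infection. The survey is sized for one overall prevalence although its population is a 1:1 mixture of two schedules, and the text should say how the arms are handled.

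Neither survey is too small for the single prevalence that it sets out to estimate, and no primary or secondary outcome is touched.

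**What to change.** Reword section 4.6 before the separate ethics submission:

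1. **Survey 1:** state 15% with 4.4 points either side (10.6% to 19.4%) for 250 tests, or reduce to 196 tests for 5 points either side. Write the plus-or-minus sign, and cite reference 46 for the 15% in women.
2. **Survey 2:** give the source of the 13% or replace it with a lower, justified value.
3. **Survey 2:** state that HBsAg prevalence will be reported by randomised arm, with the difference and its 95% confidence interval, labelled descriptive. Give the expected precision: with about 125 per arm, roughly 6 points either side of the difference if controls are at 11% and HBV0 children at 3.1% (illustrative values).

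The cost is a few sentences. No extra tests or visits are needed, because allocation is already recorded for every child.

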5 STUDY TREATMENTS

5.1 Treatment Arms

5.1.1 Description

Both groups will be vaccinated at discharge from the maternity ward or at the health center where they were recruited, or, in the case of neonates born at home, when they are brought to the health facility for their first vaccinations. All participants will receive BCG and OPV0 plus either HBV0 or no HBV0.

5.1.2 Dosage and Route of Administration

Intervention: All enrolled neonates will receive BCG (0.05 mL intradermal injection in the left deltoid region) and OPV (2 oral drops) at hospital or health center discharge, in line with national guidelines. OPV and BCG will be provided through the national vaccination program to the HNSM inclusion center. For use at the other inclusion centers, and in case of shortage of vaccines, the BHP will procure OPV and BCG for the trial via UNICEF's Procurement Services (PS), ensuring that OPV and BCG is available for daily vaccination at all trial inclusion sites. BHP has a Memorandum of Understanding with UNICEF. The intervention group will additionally receive a 10 mcg dose (in 0.5 ml suspension) of monovalent HBV0 (HepatitisB pediatric subunit vaccine, Serum Institute of India (SII))[55] intramuscularly in the anterolateral aspect of the thigh. In case the SII HBV0 vaccine cannot be acquired, Euvax B (LG Chem Ltd)[56] or BEVAC® (Biological E. Limited)[57] will be sourced. All 3 HBV0 vaccine preparations are prequalified by WHO.

6 SUBJECT ENROLLMENT AND RANDOMIZATION

6.1 Recruitment

All unvaccinated and healthy neonates will be eligible for the trial provided that written informed consent is obtained and they fulfil none of the exclusion criteria. Eligibility screening will occur at the recruitment centers, either at discharge from the Maternity ward or when neonates are brought there for their first neonatal vaccines. Neonates born at home, presenting at a recruitment center, are thus eligible if they are less than 1 week old (<8 days of age). Informed written consent will be obtained from mothers/guardians following an oral explanation of the trial in Portuguese Creole and a written explanation in Portuguese. Participation is voluntary, and families may withdraw from the trial at any time. If the family declines to participate or the child is not eligible for any other reason, the inclusion team will offer to vaccinate the child with BCG and OPV, unless there are known contraindications for vaccination.

6.2 Eligibility Criteria

6.2.1 Inclusion Criteria

Neonates can be enrolled if they are present at one of the recruitment centers, are clinically stable and the neonate's family (mother, father or guardian) has provided informed consent for participation.

6.2.2 Exclusion Criteria

Participants fulfilling any of the following will be excluded:

- Age more than 1 week (≥ 8 days of age).
- Already received any vaccine.
- Is moribund as determined by the BHP inclusion supervisor or the staff at the inclusion center.
- Has a major visible malformation.
- The mother is a known hepatitis B carrier, in which case the neonate will be immediately vaccinated with BCG, OPV0 and HBV0 by our team.
- Twins of three or more.

6.3 Randomization Procedures

After informed consent has been obtained, enrolment data will be documented on a written Case Report Form (see below). From a collection of sealed randomization envelopes, prepared in blocks of 24 and stratified by sex and place of inclusion, the mother selects a sealed envelope allocating the neonate 1:1 to the intervention group (HBV0), or the control group (no 3rd vaccine). To avoid confusion at subsequent follow-up, twins of the same sex are only randomized once and allocated the same treatment (the mother only draws one sealed randomization envelope), whereas twins of different sex each will be randomized according to their sex.

6.4 Blinding Arrangements

Since there is no placebo vaccine, the inclusion teams at each inclusion center will not be blinded to the randomization allocation and the mother/guardian will be informed of the randomization allocation. However, all outcome assessors involved in follow-up procedures will be blinded, ensuring objective outcome assessment while maintaining operational feasibility in the setting. The senior trial statistician, who will conduct the final analysis of the trial data, will be blinded to the randomization allocation until the DSMB decides to unblind the trial.

6.5 Breaking of the Study Blinding

The trial statistician will be blinded until the DSMB decides to unblind the trial.

6.6 Subject Withdrawal

Because HBV0 is given in a single dose, the parents will not be able to withdraw their child from treatment except within the short time interval between randomization and vaccination. Consent can be withdrawn for follow-up procedures. Participants whose parents withdraw consent for their child's data to be used will not count towards the total number of participants, and they will not receive further follow-up calls or home visits.

6.7 Protocol Violations

Protocol violations will be recorded throughout the trial for participants in both treatment arms; they will be recorded in a trial log along with all other major events (e.g., health care system strikes, milestones, vaccine campaigns, and any other important observations).

6.8 Trial Closure

In principle, the trial is powered to be completed when 7,250 eligible newborns have been enrolled in each arm of the trial. In practice, we will continue enrollments until the Health Ministry of Guinea-Bissau introduces universal HBV0 or when 12,500 eligible newborns have been enrolled in each arm of the trial, whichever comes first.

7 ADVERSE EVENTS

BCG can cause axillary lymphadenitis, and very rarely this can ulcerate. Very rarely, in an infant with severe immunodeficiency, BCG can cause disseminated infection (*BCGitis*). OPV can cause vaccine-associated paralytic poliomyelitis diarrhea, fatigue and muscle weakness. For HBV0, the most common reactions are mild soreness, erythema, induration, fatigue, fever, malaise, and influenza-like symptoms. Less common systemic reactions include nausea, vomiting, diarrhea, abdominal pain, abnormal liver function tests, arthralgia, myalgia, rash, pruritus, urticaria.[58] All the listed adverse events are rare or very rare. All three vaccines can cause allergic reactions in very rare circumstances. Each inclusion team will have adrenalin available along with guidelines for medical therapy to handle an acute anaphylactic reaction. All adverse events are captured through the outcome data collection.

8 STATISTICAL METHODS

8.1 Population to be analyzed

Data analysis will be conducted as intention-to-treat including all participants as randomized, apart from participants whose parents have withdrawn consent for their child's data to be used as part of this study, who will be excluded from analysis.

8.2 Statistical Analysis

The Statistical Analysis Plan (SAP) will be drafted by the trial group and submitted to the DSMB for approval. Upon approval and before initiation of data analysis, the SAP will be uploaded to an online repository. When requested by the DSMB, the trial data can be unblinded, analyzed and reported according to the SAP.

The primary endpoint for the trial will be the composite outcome of all-cause mortality and first non-fatal infectious disease admission up to 42 days of age with censoring at the time of an event, loss to follow-up, or by 42 days of age, whichever comes first. Cumulative curves for mortality and hospitalization risk will be computed using the mean cumulative function, overall, and by sex. Person-years of risk will be calculated from enrollment (day, hour and minute of randomization).

The risk of the single-event composite outcome (all-cause mortality or first non-fatal admission with infection) will be estimated using Cox proportional hazards models with age as the underlying time scale, thus inherently adjusted for age. The Cox models will provide hazard ratios (HRs) from single-event analyses of the composite outcome (all-cause mortality or first non-fatal admission with infection) up to 42 days of age (primary endpoint). Incidence rate ratios for secondary endpoints relating to long-term follow-up for mortality and admissions will be estimated using recurrent-event Andersen-Gill Cox proportional hazards models with robust standard errors. Infants will not be considered at risk of admission while admitted. Randomization will be stratified by sex and place of enrollment in blocks of 24; we will therefore include different underlying baseline hazard functions by sex and place of enrollment in the Cox models. The Cox regression models will have age as the underlying time scale and account for the survival interdependency among twin pairs by using the Stata cluster command.

Tests for proportionality of hazard rates will be computed using Schoenfeld residuals, and by visual inspection of cumulative risk curves drawn using the Kaplan-Meier method.

In-hospital case-fatality risk will be estimated using binomial regression providing risk ratios (RRs), also using the Stata cluster command. In case there are fewer than five events in one group, Fisher's exact test will be used to compute a p-value.

Cognitive scores will be standardized and tested using linear regression models.

The cumulative incidence of atopic dermatitis will be separately investigated for self-reported cases and physician-diagnosed cases using binomial regression providing RRs, also using the Stata cluster command.

All analyses will be done overall and by sex using Stata software (StataCorp, College Station, Texas), with all estimates reported with 95% confidence intervals.

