A meta-analysis of three randomized controlled trials (RCTs) in Guinea-Bissau reported that administration of BCG-Denmark given soon after birth reduced neonatal mortality in low-birth-weight newborns by 38% (95% CI 17% to 54%) with infections and most notably neonatal sepsis accounting for the excess deaths among controls.[1,2] In addition, there tended to be fewer hospital admissions with sepsis by 6 weeks of age among neonates randomized to BCG at birth.[2] The beneficial effect of BCG-Denmark lasted until a different vaccine was given at 6 weeks of age. The first dose of OPV0 has been shown to further reduce mortality when given with BCG during the first two days of life, the mortality reduction comparing BCG+OPV vs BCG alone being 42% (10%-62%).[15] This effect was especially evident for males and OPV was especially efficacious against fatal respiratory infections.[16] The findings regarding BCG led to national vaccine policy changes in Guinea-Bissau and inspired related research globally.[4,17–24] In a recent cluster-RCT from Guinea-Bissau, providing BCG + OPV0 at home visits within 72 hours of birth was associated with a 59% (8%-82%) reduction in early infant mortality, when compared with home visits without provision of vaccines.[23] A recent RCT from India in babies weighing below 2,000 g reproduced the finding of significantly fewer cases of fatal neonatal sepsis and reduced all-cause mortality risk when BCG + OPV was provided shortly after birth, compared with vaccination at discharge.[24]

Hepatitis B. Hepatitis B virus is a major global health concern, not least in sub-Saharan Africa, where it is a leading cause of chronic hepatitis, cirrhosis and fatal liver cancer.[25–27] Infection acquired perinatally from mother to child (vertical transmission) or during early childhood (horizontal transmission) carries an elevated risk of chronic infection and severe disease downstream.[27]

Hepatitis B vaccination. Hepatitis B vaccination at birth (**HBV0**) is the most effective approach to prevent vertical transmission[27] and pentavalent vaccines provided at 6, 10, and 14 weeks of age provide protection against horizontal hepatitis B transmission.[28]

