4.4 Number of Subjects (Sample Size)

Based on a recently completed trial of BCG-Denmark+OPV0 vs BCG-Bulgaria+OPV0[6], conducted with the proposed setup and follow-up methodology, we anticipate a 6-week mortality rate of 1.4% and a non-fatal infectious disease admission rate of 2.6%, for a composite risk of 4% in the control group. The number of dropouts in previous trials has been low, and the composite risk of 4% is based on the collected data in the most recent trial[6], e.g., the rate accounts for loss to follow-up. If the rate of the composite outcome of all-cause mortality and non-fatal hospital admission with infection is 4% (0.04) in the control group, and HBV0 increases the rate of the composite outcome by 25% (to $1.25 \times 0.04 = 0.05$) or decreases the rate by 22% (to $0.78 \times 0.04 = 0.0312$), to have 80% power to detect such changes for the primary outcome, with alpha error <0.05, the required sample size is 14,368 newborns, 7,184 in each group, from sampsi .050 .040, a(0.05) p(0.80) and sampsi .040 .0312, a(0.05) p(0.80) in Stata/BE version 18.0. For simplicity, enrolling 14,500 newborns is expected to be possible before HBV0 is introduced in Guinea-Bissau. With a composite outcome prevalence of 4% (0.04), the number of deaths and non-fatal infectious disease admission expected is $7,250 \times 0.04 = 290$. With 290 events in the control group, expected to be reached when 7,250 newborns have been recruited in each trial arm, the trial has 80% power to detect if HBV0 has a beneficial non-specific effect, decreasing the rate of the primary outcome by $\geq 22\%$ or a detrimental non-specific effect, increasing the rate by $\geq 24\%$. This design ensures statistical power and precision to detect also minor NSEs of HBV0, with no known disadvantages to participants. The exact timepoint that the trial will end is determined by the time when the Ministry of Health introduces HBV0 in Guinea-Bissau. We will therefore continue the trial until HBV0 is introduced in Guinea-Bissau or when 25,000 neonates have been enrolled in the trial, whichever comes first. If 25,000 neonates are enrolled in the trial, we will be able to detect an increase in the rate of the composite outcome of 18% and a decrease of 17%.

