8.3 Subgroup Analyses

For mortality and morbidity outcomes, there will be assessment of outcomes by other ages and of outcomes assessed in more specific ways, as also outlined above.

- The composite outcome of all-cause mortality and non-fatal admission with infection by 42 days of age and by 2 years of age
- All-cause mortality by 42 days of age and 2 years of age.
- In-hospital case-fatality for all-cause and infectious disease admissions by 42 days of age and 2 years of age.
- Morbidity: hospital admissions and in-hospital case-fatality rate for major diseases groups (sepsis, respiratory infections, bronchitis, diarrheal diseases, malaria, malnutrition-related diseases) by 42 days of age and by 2 years of age.

Potential effect modification

Based on literature-identified potential effect modifiers, we will assess whether the effect of HBV0 is modified by the following potential effect modifiers (in addition to sex): vaccination campaigns, the BCG scar status of the mother at enrollment, inclusion weight ($\geq 2,500\text{g}$, between $\geq 2,000\text{g}$ to $<2,500\text{g}$, and $<2,000\text{g}$), season, mode of delivery (vaginal or Caesarean section) and whether the baby was born at a hospital or elsewhere. We will conduct a supplementary analysis to assess

HBV0's effects by age at enrolment (within 24 hours and ≥ 24 hours after birth), our hypothesis being that HBV0 will have the most marked effects among the youngest neonates. For the composite outcome by 42 days of age and by 2 years of age, we will calculate the female/male ratio.

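### The 2-year mortality, composite and admission ratios average over the 42-day point, and no effect after 42 days is estimated

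*Protocol*

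**What the plan says.** Section 8.2 of the protocol gives the 42-day composite a single-event Cox model. For long-term mortality and admissions it specifies "recurrent-event Andersen-Gill Cox proportional hazards models with robust standard errors". Person-time starts at randomization, age is the time scale, and no treatment-by-period term or second start of follow-up is named. Proportionality is to be checked with Schoenfeld residuals and by inspecting curves, without saying what follows if it fails.

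Section 8.3 lists the windows: "The composite outcome of all-cause mortality and non-fatal admission with infection by 42 days of age and by 2 years of age". All-cause mortality and admissions by disease group have the same two horizons, and Table 2 in section 4.3 agrees. All of them are cumulative.

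Three places bear on day 42:
- Section 3.1 ends the primary window there because the next routine vaccines are then due.
- Figure 2 (section 2.2) shows both arms receiving the same 6-week vaccines, including DTP-HepB-Hib1.
- Section 2.1 reports that the benefit of BCG-Denmark "lasted until a different vaccine was given at 6 weeks of age".

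**The concern.** Before 42 days the arms differ in whether the infant has had any hepatitis B vaccine. From the 6-week visit controls receive it too, so the contrast becomes an extra birth dose against none, on top of a shared schedule. One ratio from enrollment to 2 years mixes these two situations. Its value depends on how many events fall on each side of day 42, and the protocol gives no figure for the later side.

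The loss is in interpretation. A 2-year ratio somewhat above 1 could mean an early effect that stopped, or a weak effect that persisted. A ratio near 1 could mean no effect, or two opposite effects. Section 12 gives uncertainty about both short-term and long-term broader effects as a reason for the trial, so the later period is of interest in its own right. A reader cannot recover a later HR with a confidence interval from two overlapping cumulative HRs.

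**Working it through.** **Inputs from section 4.4.** The control risk to 42 days is stated in "for a composite risk of 4% in the control group", which is 290 control events among 7,250. The early effects are those of the sample size calculation: "HBV0 increases the rate of the composite outcome by 25" percent (ratio 1.25), or "decreases the rate by 22" percent (ratio 0.78). Alpha is 0.05 two-sided and power is 80%.

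**Assumed input.** k = control events from 42 days to 2 years divided by control events to 42 days. The protocol gives no basis for k, so it is varied from 0.5 to 3 (145 to 870 late control events).

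**Step 1: reproduce the plan's sample size.** For 0.04 against 0.0312, with mean 0.0356:

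n = [1.96·√(2·0.0356·0.9644) + 0.8416·√(0.04·0.96 + 0.0312·0.9688)]² / 0.0088² = 6,959 per arm.

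With continuity correction, n·[1 + √(1 + 4/(n·0.0088))]²/4 = 7,184 per arm, or 14,368 in total. This matches section 4.4. The protocol states no power or event figure for the 2-year analyses.

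**Step 2: averaged ratio.** With similar numbers at risk in each arm, the single ratio is close to

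(290·HR_early + 290·k·HR_late) / (290·(1 + k)).

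Power is Φ(|ln HR|·√(D/4) − 1.96), where D is total events. With HR_late = 1.0:

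| k | Early 1.25: 2-year HR | D | Power | Early 0.78: 2-year HR | D | Power |
|---|---|---|---|---|---|---|
| 0 (42-day analysis) | 1.25 | 652 | 81% | 0.78 | 516 | 81% |
| 0.5 | 1.17 | 942 | 66% | 0.85 | 806 | 62% |
| 1 | 1.13 | 1,232 | 54% | 0.89 | 1,096 | 49% |
| 2 | 1.08 | 1,812 | 40% | 0.93 | 1,676 | 34% |
| 3 | 1.06 | 2,392 | 32% | 0.945 | 2,256 | 27% |

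For example, at k = 1: (362.5 + 290)/580 = 1.125. A simulation of a two-period, first-event Cox likelihood with 7,250 per arm gave 1.13, 1.09 and 1.07 for k = 1, 2 and 3, in agreement.

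As an illustration only, 1.25 followed by 0.80 at k = 1 gives (362.5 + 232)/580 = 1.025, with about 6% power.

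**Step 3: what a split would give.** The early estimate is unchanged. If the later HR is 1.0, its 95% CI is the estimate multiplied and divided by exp(1.96·√(2/(290k))): 1.26, 1.18, 1.12 and 1.10 for k = 0.5, 1, 2 and 3.

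The log difference between the periods (1.25 early, 1.0 late) has SE √(1/290 + 1/362.5 + 2/(290k)):
- k = 1: SE 0.114, ln 1.25/SE = 1.95, power about 50%.
- k = 2: SE 0.098, ln 1.25/SE = 2.27, power about 62%.

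**Limits.** The averaged ratio depends only on k and the two HRs, so Step 2 applies to mortality or admissions with their own k. The power figures are for the composite and treat events as independent. In the Andersen-Gill model repeat admissions count as events, which can raise k, and the robust standard errors would then be wider than these.

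**The case against.** The strongest reply is that nothing here is misstated. The comparison from randomization to 2 years includes all randomized infants, accords with the intention-to-treat principle in section 8.1, and answers a fair question about overall health. A later HR is conditional on survival to 42 days, which is a post-randomization event. Curves and Schoenfeld tests might reveal a change over time, section 8.3 speaks of assessment at other ages, and a period split may be in the statistical analysis plan, which is not shown.

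Much of this stands. The 0–2 year contrast is valid and should stay. What remains is that the protocol itself fixes the model, the start of risk time and the windows. The only ages it then lists are 42 days and 2 years, and neither a proportionality test nor a curve yields a later HR with an interval.

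Stronger readings are tempting, and the document does not support them:
- *The protocol expects the HBV0 effect to change at 42 days.* It does not say so. The sentence on duration concerns BCG-Denmark, a live vaccine, and section 2.1 says non-specific effects of HBV0 have never been studied. Closing the primary window before the next vaccines avoids interference from them and predicts nothing about later effects.
- *A real early effect would be lost.* It would not: the 42-day composite is primary, and mortality and admissions are also reported to 42 days.
- *The 2-year result is offered as independent confirmation.* Table 2 lists it openly as a further age for the same outcome.

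**Conclusion.** The point holds as a minor improvement to secondary analyses. As written, the 2-year mortality, composite and admission results are each one ratio averaged over 42 days of age, and no effect after 42 days is estimated. If an early HR of 1.25 is followed by 1.0, the 2-year ratio is about 1.13 or 1.08 when late control events are one or two times the early ones; an early 0.78 becomes 0.89 or 0.93. These sizes rest on an assumed late-to-early event ratio and on an assumed change at day 42, which the choice of window and the BCG precedent make plausible but do not establish. The primary endpoint, its analysis and the sample size are not touched. In-hospital case-fatality uses binomial regression and lies outside the point.

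**What to change.** Keep the overall 0–2 year ratio as the cumulative estimate. In the same Andersen-Gill models, split follow-up at 42 days of age with a treatment-by-period term. Report the HR from 42 days to 2 years with its confidence interval beside the 0–42 day HR, and a test of the difference. Split on age rather than on the date the 6-week vaccines were received, because receipt follows randomization.

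No new data are needed. The costs are modest. The later HR is conditional on survival to 42 days; with 1.4% mortality expected, about 98.6% of controls reach it. It is also less precise than the overall ratio. The test of the difference has only about 50% to 62% power in the scenarios above, so a non-significant result should not be read as a constant effect, and the period estimates should be reported either way.
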